### 8.1.3 Outcome Categorization

The outcome of AEs must be recorded during the course of the study in the eCRF. Outcomes are as follows:

- Fatal

- Not recovered/not resolved
- Recovered/resolved
- Recovered/resolved with sequelae
- Recovering/resolving
- Unknown

#### **8.1.4 Symptoms of the Disease Under Study**

Symptoms of the disease under study should not be classified as AEs as long as they are within the normal day-to-day fluctuation or expected progression of the disease and are part of the efficacy data to be collected in the study; however, significant worsening of the symptoms should be recorded as an AE. Specifically, SE signs and symptoms that were present at study entry and that varied in intensity over the duration of study treatment are not considered AEs unless in the investigator's opinion there is an *unexpected* worsening of the events. However, if all seizure activity resolved and the subject returned to baseline status, but SE recurred, the event would then be recorded as an SAE.

#### **8.1.5 Clinical Laboratory and Other Safety Evaluations**

A change in the value of a clinical laboratory, vital sign, or ECG assessment can represent an AE if the change is clinically significant or if, during treatment with the study drug, a shift of a parameter is observed from a normal value to an abnormal value, or there is a further worsening of an already abnormal value. When evaluating such changes, the extent of deviation from the reference range, the duration until return to the reference range (either while continuing treatment or after the end of treatment with the study drug), and the range of variation of the respective parameter within its reference range must be taken into consideration.

For subjects who complete the study and don't progress to an IV anesthetic drug (a 3rd line treatment) for seizure suppression, if, at the end of the treatment phase, there are abnormal clinical laboratory, vital sign, or ECG values that were not present in the pretreatment findings observed closest to the start of study drug initiation, further investigations should be performed until the values return to within the reference range or until a plausible explanation (e.g., concomitant disease) is found for the abnormal values.

The investigator should decide, based on the above criteria and the clinical condition of a subject, whether a change in a clinical laboratory, vital sign, or ECG parameter is clinically significant and therefore represents an AE.

#### **8.1.6 Pregnancy**

As this study allows for pre-consenting of subjects, all pregnancies are to be reported from the time of first dose of study drug until the defined follow-up period stated in Section 7.1.3.

Any report of pregnancy for any female study participant or the partner of a male study participant must be reported within 24 hours to the Marinus Safety Department or its delegate

using the Pregnancy Report Form. A copy of the Pregnancy Report Form (and any applicable follow-up reports) must also be sent to the CRO/Marinus Medical Monitor using the details specified in the emergency contact information section at the beginning of the protocol. If a subject has a positive test result, it will be at the investigator's discretion to weigh the risks versus benefits for the subjects continued participation.

Every effort should be made to gather information regarding the pregnancy outcome and condition of the infant. It is the responsibility of the investigator to obtain this information within 30 calendar days after the initial notification and approximately 30 calendar days after delivery.

Pregnancy complications such as spontaneous abortion/miscarriage or congenital abnormality are considered SAEs and must be reported as outlined in Section 8.2 of the protocol using the Marinus SAE Fax Cover Letter. Non-serious AEs are to be reported as per clinical electronic Case Report Form guidelines. Note: An elective abortion is not considered an SAE.

In addition to the above, if the investigator determines that the pregnancy meets serious criteria, it must be reported as an SAE to the Marinus Safety Department or delegate as outlined in Section 8.2 of the protocol using the Marinus SAE Fax Cover Letter. The test date of the first positive serum/urine  $\beta$ -human chorionic gonadotropin test or ultrasound result will determine the pregnancy onset date.

#### **8.1.7 Abuse, Misuse, Overdose, and Medication Error**

Abuse, misuse, overdose, or medication error (as defined below) must be reported to the sponsor per the SAE reporting procedure whether or not it results in an AE/SAE as described in Section 8.2. Note: The 24-hour reporting requirement for SAEs does not apply to reports of abuse, misuse, overdose, or medication errors unless these result in an SAE.

The categories below are not mutually exclusive; the event can meet more than one category.

- Abuse: Persistent or sporadic intentional intake of a study drug for a nonmedical purpose (e.g., to alter one's state of consciousness or get high) in a manner that may be detrimental to the individual and/or society.
- Misuse: Intentional use of a study drug other than as directed or indicated at any dose. (Note: This includes a situation in which the study drug is not used as directed at the dose prescribed by the protocol.)
- Overdose: Intentional or unintentional intake of a dose of a study drug exceeding a prespecified total daily dose of the product.
- Medication error: An error made in prescribing, dispensing, administering, and/or use of a study drug. For studies, medication errors are reportable to the sponsor only as defined below.

Cases of subjects missing doses of the study drug are not considered reportable as medication errors.

Medication errors should be collected and reported for all products under investigation.

The administration and/or use of an expired study drug should be considered as a reportable medication error.

All study drug provided in this study will be administered by appropriate site staff.

## **8.2 Serious Adverse Event Procedures**

### **8.2.1 Reference Safety Information**

The reference for safety information for this study is the Ganaxolone Investigator's Brochure, which the sponsor has provided under separate cover to all investigators. However, the Investigator's Brochure has not been updated with the details of the 1 mg/mL ganaxolone IV solution. The formulation details have been added to Section 6 and will be added to the Investigator's Brochure at the annual update.

### **8.2.2 Reporting Procedures**

All initial and follow-up SAE reports must be reported by the investigator to the Marinus Safety Department or its delegate and the CRO/Marinus Medical Monitor within 24-hours of the first awareness of the event. Note: The 24-hour reporting requirement for SAEs does not apply to reports of abuse, misuse, overdose, or medication errors (see Section 8.1.7) unless they result in an SAE.

The investigator must complete, sign, and date the Marinus SAE Fax Cover Letter and verify the accuracy of the information recorded on the form with the corresponding source documents (Note: Source documents are not to be sent unless requested) and fax or e-mail the form to the Marinus Safety Department or its delegate. A copy of the Marinus SAE Fax Cover Letter (and any applicable follow-up reports) must also be sent to the CRO/Marinus Medical Monitor using the details specified in the emergency contact information section of the protocol.

### **8.2.3 Serious Adverse Event Definition**

An SAE is any untoward medical occurrence (whether considered to be related to study drug or not) that at any dose:

- Results in death
- Is life-threatening. Note: The term "life-threatening" in the definition of "serious" refers to an event in which the subject was at risk of death at the time of the event; it does not refer to an event that hypothetically might have caused death if it were more severe.
- Requires in-patient hospitalization or prolongation of existing hospitalization. Note: Hospitalizations, which are the result of elective or previously scheduled surgery for preexisting conditions that have not worsened after initiation of treatment, should not be classified as SAEs. For example, an admission for a previously scheduled ventral hernia repair would not be classified as an SAE; however, a complication resulting from a

hospitalization for an elective or previously scheduled surgery that meets serious criteria must be reported as an SAE.

- Results in persistent or significant disability or incapacity
- Is a congenital abnormality or birth defect
- Is an important medical event. Note: Important medical events that may not result in death, be life-threatening, or require hospitalization may be considered an SAEs when, based on appropriate medical judgment, they jeopardize the patient and may require medical or surgical intervention to prevent one of the outcomes listed in this definition. Examples of such medical events include allergic bronchospasm requiring intensive treatment in an emergency room or at home; blood dyscrasias or convulsions that do not result in in-patient hospitalization; or the development of drug dependency or drug abuse.

#### **8.2.4 Serious Adverse Event Collection Time Frame**

As this study allows for pre-consenting of subjects, all SAEs (regardless of relationship to study) are collected from the time of first dose of study drug until the defined follow-up period stated in Section 7.1.3 and must be reported to the Marinus Safety Department and the CRO/Marinus Medical Monitor within 24-hours of the first awareness of the event.

In addition, any SAE considered “related” to the study drug and discovered by the investigator at any interval after the study has completed must be reported to the Marinus Safety Department within 24 hours of the first awareness of the event.

#### **8.2.5 Serious Adverse Event Onset and Resolution Dates**

The onset date of the SAE is defined as the date the event meets serious criteria. The resolution date is the date the event no longer meets serious criteria, the date the symptoms resolve, or the date the event is considered chronic. In the case of hospitalizations, the hospital admission and discharge dates are considered the onset and resolution dates, respectively.

In addition, any signs or symptoms experienced by the subject after study drug initiation or leading up to the onset date of the SAE, or following the resolution date of the SAE, must be recorded as an AE, if appropriate.

#### **8.2.6 Fatal Outcome**

Any SAE that results in the subject’s death (i.e., the SAE was noted as the primary cause of death) must have fatal checked as an outcome, with the date of death recorded as the resolution date. For all other events ongoing at the time of death that did not contribute to the subject’s death, the outcome should be considered not resolved, without a resolution date recorded.

For any SAE that results in the subject’s death or any ongoing events at the time of death, unless another study drug action was previously taken (e.g., the drug was interrupted, reduced, or withdrawn), the action taken with the study drug should be recorded as “dose not changed” or “not applicable” (if the subject never received the study drug). The study drug action of “withdrawn” should not be selected solely as a result of the subject’s death.

## **8.2.7 Regulatory Agency, Institutional Review Board, Ethics Committee, and Site Reporting**

The sponsor or its delegate is responsible for notifying the relevant regulatory authorities in the United States of related, unexpected SAEs.

In addition, the sponsor or its delegate is responsible for notifying active sites and central IRBs of all related, unexpected SAEs occurring during all interventional studies across the Ganaxolone program.

The investigator is responsible for notifying the local institutional review boards (IRBs), local ethics committee (EC), or the relevant local regulatory authority of all SAEs that occur at their site as required.

## **9. DATA MANAGEMENT AND STATISTICAL METHODS**

### **9.1 Data Collection**

The investigator's authorized site personnel must enter the information required by the protocol in the eCRF. A study monitor will visit each site in accordance with the monitoring plan and review the eCRF data against the source data for completeness and accuracy. Discrepancies between source data and data entered in the eCRF will be addressed by qualified site personnel. When a data discrepancy warrants correction, the correction will be made by authorized site personnel. Data collection procedures will be discussed with the site at the site initiation visit and/or at the investigator's meeting. Once a subject is enrolled, the site should initiate data entry within 5 business days of study drug initiation with the goal of having all data entered within 4-weeks of study drug initiation.

### **9.2 Clinical Data Management**

Data are to be entered into a clinical database as specified in the CRO Data Management Plan and the eCRF Completion Guidelines. Quality control and data validation procedures are applied to ensure the validity and accuracy of the clinical database.

Data are to be reviewed and checked for omissions, errors, and values requiring further clarification using computerized and manual procedures. Data queries requiring clarification are to be communicated to the site for resolution. Only authorized personnel will make corrections to the clinical database, and all corrections are documented in an auditable manner.

### **9.3 Statistical Analysis Process**

The study will be analyzed by the sponsor or its agent.

The statistical analysis plan (SAP) will provide the statistical methods and definitions for the analysis of the efficacy and safety data, as well as describe the approaches to be taken for summarizing other study information, such as subject disposition, demographics, and baseline characteristics, study drug exposure, and prior and concomitant medications. The SAP will also include a description of how missing, unused, and spurious data will be addressed.

To preserve the integrity of the statistical analysis and study conclusions, the SAP will be finalized prior to database lock and the sponsor being unblinded to treatment assignments.

All statistical analyses will be performed using SAS® (SAS Institute, Cary, NC 27513). R (R Foundation for Statistical Computing) may be used for the predictive probability calculations used in the interim analyses.

#### **9.4 Sample Size, Planned Interim Analysis, Adaptive Design, and Data Monitoring Committee**

Data from the open-label group will be summarized using descriptive statistics and not included in double-blind efficacy analysis.

In the double-blind group, the response rates in the treatment and control groups will be compared using a 1-sided hypothesis test. An O'Brien-Fleming error spending function will be used with two predefined interim analyses. The two interim analyses will occur after approximately 156 and 200 subjects have completed 24-hours of study drug administration. Prior to initiating these pre-planned analyses, the data for these subjects will have a minimum of their critical fields cleaned.

Using a total one-sided Type I error of 2.5%, critical values for the two interim and one final analysis are noted in Table 6.

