### **5.2.2 Prohibited Treatment**

As per the exclusion criterion in Section 4.2, the only allowable concurrent 2nd line IV AED therapies to treat the current episode of SE are fosphenytoin/phenytoin, valproic acid, levetiracetam, lacosamide, or brivaracetam. Administering fosphenytoin and/or phenytoin will be counted as one (1) AED. These drugs can be used alone or in combination with each other. If the subject is receiving oral AED therapy to manage a subject's chronic medical condition, for example, epilepsy, migraine, or neuropathic pain, that therapy is acceptable and should continue unchanged, if feasible and medically justified. This prophylactic treatment does not count towards the SE treatment failures required to qualify for this study. If any of these oral AED medications had to be interrupted around the time of the current SE episode, it is recommended that they would be re-started 10 hours after study drug initiation, if medically acceptable. Also, subjects who have been enrolled in another clinical study for SE are required to have a reasonable expectation that the other investigational drug has been cleared from their system, that is, that five half-lives have elapsed. Subjects on IV AEDs that are standard of care can be enrolled in the study. Subjects who have taken exogenous allopregnanolone or ganaxolone previously are not eligible for the study.

If a subject progresses at any time during the study to an IV anesthetic drug (a 3rd line treatment; e.g. midazolam, propofol, thiopental, pentobarbital, or ketamine and/or 4th line treatment; e.g., immunosuppressants, magnesium) for seizure suppression, study drug administration will be discontinued, however the subject will continue with the in-patient follow-up day and the week 2, 3, and 4 follow-up visits.

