### Scenarios for stopping the study drug without a taper include:

- For subjects who receive study drug for less than 2 hours and/or
- Study drug infusion is discontinued or interrupted, and the decision is made to not restart the infusion and/or
- If at any time during study drug administration the subject progresses to an IV anesthetic drug (a 3rd line and/or 4th line treatment) for seizure suppression or
- It is no longer safe to continue drug administration per the investigator’s medical judgment.

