**Table 6: Interim Analysis Variables**

Analysis	# Subjects who completed the study anytime within 24 hours of study drug administration	One-sided Critical Value	Error Spend	Cumulative Error Spend
Interim 1	156 subjects	0.0073	0.0073	0.0073
Interim 2	200 subjects	0.0135	0.0083	0.0156
Final	242 subjects	0.0200	0.00935	0.025

In the double-blind group a Data Monitoring Committee (DMC) will be assembled to review the safety and efficacy data at various intervals of the study. Only the unblinded DMC will be privy to these interim analyses and may recommend the trial stop for early success or safety findings.

Likewise, at each interim analysis, Bayesian predictive probabilities for success at the maximum (N=242) sample size will be calculated. If the predictive probability of success is < 5%, then the DMC may recommend the trial stops for futility. These are non-binding futility analyses, e.g., the Type I error = 2.5% even without these futility analyses. The Bayesian predictive probabilities will use non-informative Beta (1/2, 1/2) priors for both unknown response rates and be conducted using the methodology described in Saville et al., 2014 (Clinical Trials).

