## 9.5 Sample Size Calculation and Power Considerations

The double-blind sample size was constructed to offer at least 85% power with a 20% effect.

Table 7 shows the power for a control group response rates ranging from 30% to 70% and assuming a 20% improvement in the treatment group.

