## 9.7 Efficacy Analyses

### 9.7.1 Primary Efficacy Endpoint

The primary efficacy endpoint is defined as the number of subjects who did not require an IV anesthetic drug (a 3rd line treatment) for SE treatment within the first 24 hours after study drug initiation.

The primary efficacy analysis will be conducted over the mITT Set. The primary efficacy analysis will be conducted by using a logistic model that includes treatment group as a factor along with factors controlling for age, GCS, and history of epilepsy. One-sided tests will be performed and compared to the critical values shown in Section 9.4, thus ensuring overall 1-sided Type I error  $\leq 0.025$ .

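### The Section 9.4 interim trigger counts only subjects who complete 24 hours of study drug, so primary-endpoint failures never count and the looks fall late or not at all

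*Protocol*

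**What the plan says.** Protocol Section 9.4 plans two interim analyses and a final one: "The two interim analyses will occur after approximately 156 and 200 subjects have completed 24-hours of study drug administration". It then says that critical fields will be cleaned for those subjects before each look. The Table 6 column that holds the counts 156, 200 and 242 is headed differently: "Subjects who completed the study anytime within 24 hours of study drug administration".

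Section 9.7.1 defines the outcome: "The primary efficacy endpoint is defined as the number of subjects who did not require an IV anesthetic drug" for SE treatment "within the first 24 hours after study drug initiation". An IV anesthetic given for SE inside that window is therefore a failure.

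Section 5.2.2 states what happens to study drug when a subject moves to an IV anesthetic "for seizure suppression, study drug administration will be discontinued, however the subject will continue with the in-patient follow-up day". Section 6.2.3 repeats this in its list of reasons to stop without a taper: "If at any time during study drug administration the subject progresses to an IV anesthetic drug". In the double-blind group study drug means ganaxolone or placebo, so the rule applies to both arms.

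**The concern.** The event that defines failure also ends study drug before hour 24. A subject who fails within 24 hours cannot complete 24 hours of study drug, and so cannot enter the count that triggers a look. Responders who stop early for safety or operational reasons drop out of the count as well.

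Table 6 does not repair this. Under Section 3.2 participation lasts about four weeks, and subjects who stop drug stay in follow-up, so nobody who remains in follow-up completes the study within 24 hours. Neither wording names the unit the design needs, which is a subject whose 24-hour outcome is known.

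At stake is when the data monitoring committee sees unblinded data. The chance of stopping early for success or futility, and the saving in sample size, both depend on the looks falling at the planned fractions of enrolment.

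**Working it through.** **Inputs.** Looks at 156, 200 and 242 with one-sided critical values 0.0073, 0.0135 and 0.0200 (Table 6); maximum 242, randomized 1:1, so 121 per arm (Section 9.4 and synopsis); "control group response rates ranging from 30% to 70% and assuming a 20% improvement in the treatment group" (Section 9.5).

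**Step 1: reproduce Table 7.** At 40/60% the table gives stopping probabilities of 0.44 at 156 and 0.22 at 200. Expected N = 156 × 0.44 + 200 × 0.22 + 242 × (1 − 0.44 − 0.22) = 68.6 + 44.0 + 82.3 = 194.9, against the stated 195. The table therefore treats 156 and 200 as total subjects, failures included.

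An exact two-binomial group-sequential calculation with 78, 100 and 121 per arm, using Fisher's exact test at the Table 6 levels, gives:
- total power 0.860, 0.853, 0.860, 0.903 and 0.967 (stated 0.86, 0.85, 0.86, 0.90, 0.97);
- expected N 190, 193, 190, 185 and 173 (stated 193, 195, 193, 187, 175);
- first-look stopping 0.488, 0.446, 0.488, 0.555 and 0.709 (stated 0.48, 0.44, 0.48, 0.56, 0.70).

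The second-look figures come out 0.03 to 0.05 higher than stated and the third-look figures 0.03 to 0.05 lower. Totals agree closely.

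**Step 2: apply the literal trigger.** Treat every responder as a 24-hour completer. This is generous, because some responders stop drug early. Completers among 242 are then Binomial(121, control rate) + Binomial(121, treatment rate), with expectation 242 × mean rate. The number randomized when k completers are expected is k / mean rate.

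| Control/treatment | Mean rate | Expected completers of 242 | P(≥156) | P(≥200) | Randomized for 156 | Randomized for 200 |
|---|---|---|---|---|---|---|
| 30/50% | 0.4 | 96.8 | <0.001 | <0.001 | 390 | 500 |
| 40/60% | 0.5 | 121.0 | <0.001 | <0.001 | 312 | 400 |
| 50/70% | 0.6 | 145.2 | 0.083 | <0.001 | 260 | 333 |
| 60/80% | 0.7 | 169.4 | 0.976 | <0.001 | 223 | 286 |
| 70/90% | 0.8 | 193.6 | >0.999 | 0.164 | 195 | 250 |

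**Step 3: timing.** The planned fractions are 156/242 = 64.5% and 200/242 = 82.6%. These are also the pooled completion rates needed to reach each trigger at all. Where Interim 1 is likely, it falls at 223/242 = 92% (60/80%) or 195/242 = 81% (70/90%). Interim 2 needs more than 242 randomized, on expectation, in every scenario.

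**Step 4: consequence.** At 40/60% neither look occurs in practice, so N is 242 instead of an expected 195, a loss of 47 subjects of expected saving. The futility statement under Table 7 (88% early stopping and expected N of 171 when the arms are equal) is affected in the same way. With a common response rate of 50% or below, P(≥156) is under 0.001; at 60% it is 0.088; at 70% it is 0.973. The protocol does not say which common rate the 88% assumes.

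Power is hardly touched. A single final Fisher test at 0.0200 with 121 per arm, summed over the two binomial distributions, gives 0.844 at 40/60%, against 0.853 with all three looks.

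**The case against.** The best reply is that the intended unit is clear from context. Table 6 uses one column for all three analyses. If it meant completers of 24 hours of drug, the final analysis would require all 242 randomized subjects to complete, that is, no failures at all. Table 7 reproduces with all subjects counted. This stands: it makes the point a wording contradiction, not a design that cannot run.

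A reader might infer that the interim data would consist almost entirely of responders and so carry no information on treatment effect. The documents do not support that. Section 9.4 sets the timing of the looks and says whose data are cleaned; it does not restrict the interim analysis set. Section 9.7.1 runs the primary analysis on the mITT Set and compares it with the Section 9.4 critical values, and Section 9.6 defines that set as everyone dosed with any post-initiation outcome data, failures included. What remains is that no section states the interim set outright.

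A reader might also infer that the looks are impossible. That is too strong. The counts in the table are expectations and not ceilings: Interim 1 is likely in two scenarios and has an 8% chance at 50/70%, and Interim 2 has a 16% chance at 70/90%.

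Finally, none of this affected the present study. SAP Sections 1, 3.1 and 4.11 say that only open-label data are analysed, that the double-blind phase was not conducted, and that there was no formal interim analysis. That also stands.

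**Conclusion.** The concern holds as a defect in the timing rule. Section 9.4 conflicts with the drug-stopping rule in Sections 5.2.2 and 6.2.3, and the Table 6 header does not resolve the conflict. Followed literally, neither look falls at its planned fraction in any Table 7 scenario, and Table 7's stopping probabilities and expected N do not describe the rule in the text. They do hold if all dosed subjects followed to 24 hours are counted. The final mITT analysis is not biased by this.

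The calculation assumes that every failure stops drug before hour 24, that every responder completes 24 hours (so the expected counts are upper bounds), and that the maximum is 242 randomized, as the protocol states. SAP Section 3.8 instead describes 242 as completed subjects out of 262 enrolled. At 262 the expected completers would be 262 × mean rate = 105, 131, 157, 183 and 210. Interim 1 would still not be expected at 30/50% or 40/60%, and Interim 2 would be expected only at 70/90%, after about 250 subjects.

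The point matters for the protocol's double-blind design and for the separate phase 3 study if this text is carried over. It has no bearing on the open-label results.

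**What to change.** In Section 9.4 and the Table 6 header, use one definition: each analysis takes place when the first 156, 200 and 242 dosed subjects have either reached 24 hours after study drug initiation or already met the primary-endpoint failure, whether or not study drug was stopped. State that each interim analysis uses the mITT set of those subjects, and that data cleaning covers all of them. Carry the same wording into the committee's charter and any phase 3 protocol built on this text.

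How to score death or withdrawal before 24 hours is a separate question that Section 9.7.1 leaves open; this rewording does not settle it.

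The cost is two wording changes and one added sentence. No sample size, critical value or power figure changes, and no extra subjects or data are needed.
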